12 COROLLARY SUB STUDY OF HIGH RISK POPULATION

In many cases TWO₂ has been shown to be particularly effective in severe wounds of multimorbid patients. Diabetic patients frequently suffer from ischemia, renal insufficiency or more severe wounds. A significant fraction of these patients use corticosteroids for other chronic diseases.

Due to the low chance of healing, a high mortality, and other reasons such as reimbursement issues these patients are normally excluded from clinical trials. However, as these patients represent an increasing percentage of all patients with diabetic ulcers we shall also include a sub study with high risk patients. In this sub study 24 patients will be randomized to either the active or the control group.

All procedures and outcomes will be the same as in the main arm of the study except for two differences:

- No biopsies will be taken
- Different inclusion and exclusion criteria

12.1 Inclusion and exclusion corollary substudy

All inclusion and exclusion criteria remain the same as in the main study population *except* the ones stated below:

INCLUSION CRITERIA

- ALL University of Texas Grades allowed *(Grade 1 and 2 in the main study)*
- ABI can be as low as 0.5 *(0.7 in the main study)*
- May have osteomyelitis *(excluded in the main study)*
- May have exposed bone *(excluded in the main study)*
- Subject may require renal dialyses *(excluded in the main study)*
- Subject may use chronic steroids *(excluded in the main study)*

EXCLUSION CRITERIA

(See previous exclusions that are now allowed in this substudy)

- Gangrene is still excluded

14 LIST OF ABBREVIATIONS AND DEFINITION OF TERMS

AE	Adverse Event
ADE	Adverse device effect
ABI	Ankle Brachial Index
AMWT	Advanced Moist Wound Therapy
AOTI	Advanced Oxygen Therapy Ltd.
CE	The initials "CE" do not stand for specific words but are a declaration by a manufacturer that a product meets the requirements of applicable European Directives.
CRF	Case Report Form
CWIS	Cardiff Wound Impact Schedule
EQ-5D	Euroqol-5D
GSD	Group Sequential Design
ICF	Informed Consent Form
ICH GCP	International Conference on Harmonization Good Clinical Practice
IEC	Independent Ethics Committee
IRB	Institutional Review Board
ITT	Intention-to-treat
mbar	Millibars
NSR	Non Significant Risk
PO2	Pressure of Oxygen
PP	Per Protocol
SADE	Serious Adverse Device Effect
SAE	Serious Adverse Event
SAP	Statistical Analysis Plan
TWO ₂	Topical Wound Oxygen
UADE	Unanticipated Adverse Device Effect

APPENDIX I

1. Study Diary Card (Example)

Next Appointment _____

Patient Name: _____

Is participating in a: Device study for Diabetic Foot Ulcers

Study Name: A Multi-national, Multi-center, Prospective, Randomized, Double Blinded, Placebo-controlled Trial to Evaluate the Efficacy of Hyperbaric Cytical Topical Oxygen Therapy (TWO₂) in the Treatment of Chronic Diabetic Foot Ulcers

The Following treatments should be avoided while on this study: antimicrobial dressings containing silver, iodine or Polyhexamethylene Biguanide (PHMB), dressings containing enzymes, and growth factors (Regranex[®] or dermal skin substitutes like Apligraf[®] or Dermagraft[®]), Hyperbaric oxygen therapy (HBO), Vacuum assisted closure (VAC), Heel therapy, Laser Therapy, Mechanical constant tension, Larval/maggot therapy (Biocelbiderment), Artificial Skin and Electrical stimulation for Tissue Repair (LS1R), Systemic antibiotic.

Please call this doctor in case of a serious medical problem or questions: _____ at _____

Thank you for your help.

FRONT

DRESSING CHANGES **TWO₂ TREATMENT (5 Days)**

Please Change your dressings: What day did you do the treatment?

Monday _____ Monday
 Tuesday _____ Tuesday
 Wednesday _____ Wednesday
 Thursday _____ Thursday
 Friday _____ Friday
 Saturday _____ Saturday
 Sunday _____ Sunday

Self Relative Nurse Home Aide Doctor Other

Please Initial: _____ Date _____

THANK YOU

BACK

2. University of Texas Wound Classification System

	I	II	III
A	Superficial Index Ulcer not involving tendon, capsule or	Index Ulcer penetrating to tendon or capsule	Index Ulcer penetrating to bone or joint
B	Infected	Infected	Infected
C	Ischemic	Ischemic	Ischemic
D	Infected and ischemic	Infected and ischemic	Infected and ischemic

3. Cardiff Wound Impact Schedule

Overall Quality of Life

We would like you to rate your overall quality of life during the past 7 days.

Please circle a number below

How good is your quality of life?

My quality of life is the worst possible 0 1 2 3 4 5 6 7 8 9 10 My quality of life is the best possible

How satisfied are you with your overall quality of life?

Not at all satisfied 0 1 2 3 4 5 6 7 8 9 10 Very satisfied

Wound Healing Research Unit

University of Wales College of Medicine

Cardiff Wound Impact Questionnaire

Overall Comments

© Copyright WHRU 1997
E:\Inetpub\wwwroot\project\1797\final version\cwinsq.doc - 28/03/2003

For Office Use

Total

© Copyright WHRU 1997

Cardiff Wound Impact Schedule, English version for the USA

The following questionnaire is concerned with the effects that your wound(s) has (have) on your daily life. Please answer the questions carefully by placing a check mark in the box which most closely reflects how you feel; it should take about ten minutes to complete.

Once a week

Less than once a month

If you are unsure about how to answer a question, please mark the answer which is closest to how you feel. All answers are confidential.

Personal Details

M F

Patient Initials

Sex

Patient Number

Date of Birth M M D D Y Y

Assessment 1st 2nd 3rd 4th 5th

Assessment Date M M D D Y Y Next Assessment Due M M D D Y Y

Wound(s) status Healed Not Healed

Do you live on your own? Yes No

How often do you see your family and friends?

Daily Once a month

© Copyright WHRU 1997
E:\Inetpub\wwwroot\project\1797\final version\cwinsq.doc - 28/03/2003

For Office Use

Total

© Copyright WHRU 1997
E:\Inetpub\wwwroot\project\1797\final version\cwinsq.doc - 28/03/2003

For Office Use

Total

Social Life

How stressful has this experience been for you during the past 7 days?

	Not at all/ Not applicable	Slightly	Moderately	Quite a bit	Very
Difficulty getting out and around					
Relying more on others					
Your family/friends being overly protective					
Unable to enjoy your usual social life (eg hobbies)					
Limited contact with family/friends					
Not going out for fear of bumping your wound site					
Wanting to withdraw from people					

Social Life

Have you experienced any of the following during the past 7 days?

	Not at all/ Not applicable	Seldom	Sometimes	Frequently	Always
Difficulty getting out and around					
Relying more on others					
Your family/friends being overly protective					
Unable to enjoy your usual social life (eg hobbies)					
Limited contact with family/friends					
Not going out for fear of bumping your wound site					
Wanting to withdraw from people					

© Copyright WHRU 1997
E:\inetpub\wwwroot\project\j1797\final version\swimsaq.doc - 28/02/2003

For Office Use

Total

© Copyright WHRU 1997
E:\inetpub\wwwroot\project\j1797\final version\swimsaq.doc - 28/02/2003

For Office Use

Total

Physical Symptoms and Daily Living

How stressful has this experience been for you during the past 7 days?

	Not at all/ Not applicable	Slightly	Moderately	Quite a bit	Very
Disturbed sleep					
Difficulty bathing					
Immobility around the home					
Immobility outside the home					
Leakage from the wound(s)					
Pain from the wound site					
Discomfort from the bandaging/dressing					
Unpleasant odor or smell from the wound(s)					
Problems with everyday tasks (eg shopping)					
Difficulty in finding appropriate footwear					
Problems with the amount of time needed to care for the wound site					
Financial difficulties as a result of the wound(s)					

© Copyright WHRU 1997
E:\inetpub\wwwroot\project\j1797\final version\swimsaq.doc - 28/02/2003

For Office Use

Total

© Copyright WHRU 1997
E:\inetpub\wwwroot\project\j1797\final version\swimsaq.doc - 28/02/2003

For Office Use

Total

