3.3.3. Safety Endpoints

Incidence, duration and severity of adverse events and device effects will be documented in every case. This includes:

- Incidence of severe infections needing hospitalization
- Malfunctioning of the device
- Worsening of the wound
- Death

3.3.4. ***Justification for Trial Design***

The choice of using the “Incidence of complete wound closure” as the primary endpoint is in accordance with the recommendation of the FDA document “*Guidance for Industry, Chronic Cutaneous Ulcer and Burn Wounds, Developing Products for Treatment*”.²³

The choice of the parallel group design is the most appropriate for a wound healing study.

The treatment duration of 12 to 16 weeks is a standard in randomized clinical trials in wound care.²⁴⁻²⁹ Two recent studies with the TWO₂ system in venous and diabetic ulcers showed that the majority of ulcers treated with topical oxygen show wound closure after 12 weeks.^{21,22}

A double blind trial is the gold standard in trial design.

Although there are a number of published reports reporting positive results on topical oxygen treatment and diabetic foot ulcers there is no comparative trial so far. In order to overcome the uncertainty surrounding the expected benefit, the trial will be undertaken using group sequential design (GSD) allowing for interim analysis to be performed at intervals during the trial recruitment.

For the purposes of standardizing to reduce treatment variability the choice of dressings for this trial will be specifically limited.

All “active” dressings will be excluded from the trial. These include: antimicrobial dressings containing silver, iodine or Polyhexamethylene Biguanide (PHMB), dressings containing enzymes, and growth factors (Regranex® or dermal skin substitutes like Apligraf® or Dermagraft®).

Adjunctive treatments such as Hyperbaric oxygen therapy (HBO), Vacuum assisted closure (VAC), Heat therapy, Laser Therapy, Mechanical constant tension, Larval/maggot therapy (Biodebridement), Artificial Skin and Electrical stimulation for Tissue Repair (ESTR) are not allowed in this study.

No local antimicrobial treatments are allowed in the study. Systemic antibiotic treatment of infection will be prescribed according to local standards.

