Histological studies in pigs treated with topical oxygen showed signs of improved angiogenesis and tissue oxygenation. Immunohistochemical analyses revealed a stronger presence of Vascular Endothelial Growth Factor (VEGF) in the tissue from oxygen treated wounds in pigs compared to the non-treated controls.¹⁷ As no studies have investigated these effects in humans, punch biopsies from 20 randomized subjects may be planned at selected centers and taken at baseline and after 4 weeks.

Recent RCTs with patients with diabetic foot ulcers from Blume et al., 2008 investigating Negative Pressure Wound Therapy versus advanced Moist Wound Therapy and the paper from Löndahl, 2010 where Hyperbaric Oxygen Therapy was evaluated as an adjunctive therapy did not exclude infected ulcers. As oxygen is critical to fight infection in chronic wounds³³⁻³⁵ and the TWO₂ device has been shown to eliminate infections and multi-resistant staphylococcus aureus (MRSA)^{21,22,36}, in this trial wound infections will not be excluded. However, any subject with wound infection must be under treatment at the time of randomization.

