4.1. Inclusion Criteria

A subject must meet all of the following criteria to be eligible for enrollment in the trial.

Ulcer characteristics

- Subject has a documented diagnosis of Diabetes mellitus Type 1 or 2
- Foot ulcer at or below ankle with duration of more than 4 weeks but no longer than 1 year
- If the index ulcer is a post amputation wound date of surgery must be > 30 days
- 2 week run in period with less than 30% wound size reduction
- University of Texas Grade 1A, 1B, 1C, 1D, 2A, 2B, 2C, or 2D (Appendix I)
- Ulcer is $\geq 1\text{cm}^2$ and $\leq 20\text{cm}^2$ after debridement at start of run-in period
- If more than one ulcer is present on the foot, only the largest is considered in the study (Index ulcer)
- Index ulcer must be $\geq 1\text{cm}$ away from any other ulcers present on the foot

Vascular status

- Adequate perfusion with ABI > 0.7 **And**
TcPO₂ > 30mmHg **OR** skin perfusion > 30mmHg **OR** Toe pressure > 30mmHg **OR**
Duplex with biphasic waveforms below the knee
- No planned revascularization procedure or vascular surgery within the last/next 30 days

Device and study related

- Males and Females 18-89 years
- Subject and/or caregiver are willing and able to comply with all specified care and visit requirements
- Subject has a reasonable expectation of completing the study; according to the Investigator's clinical judgment

4.2. Exclusion Criteria:

Ulcer characteristics

- Evidence of gangrene on any part of affected limb
- Documented evidence of osteomyelitis on any part of affected limb
- Index ulcer has exposed bone
- Index ulcer exhibits signs of severe clinical infection that requires hospitalization or immediate surgical intervention
- Active Charcot foot on the study limb

Device and study related

- Subject participated in another investigational device, drug or biological trial within last 30 days
- Uncontrolled diabetes: HbA1c > 12 %
- Renal dialysis or serum creatinine > 2.5 mg/dl
- Known immune insufficiency
- Chronic steroid use or immunosuppressive agents within the last three (3) months or is anticipated to require them during the course of the study
- Active treatment for malignancy (not specific to study limb)
- Patient has a Deep Vein Thrombosis within the last 30 days
- Subject has received growth factor therapy (e.g., autologous platelet-rich plasma gel, becaplermin, bilayered cell therapy, dermal substitute, extracellular matrix) within the screening period

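### The example study card says to avoid systemic antibiotics, which sections 3.3.4 and 6.3.4 prescribe for infection

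*Combined protocol and SAP*

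**What the plan says.** Appendix I, item 1, shows an example study card. Its front carries the line "The Following treatments should be avoided while on this study", followed by a list that ends "Artificial Skin and Electrical stimulation for Tissue Repair (LS1R), Systemic antibiotic". The item has no qualifier. The same side gives a contact: "Please call this doctor in case of a serious medical problem or questions".

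The body of the protocol has a different rule. Section 3.3.4 states: "No local antimicrobial treatments are allowed in the study. Systemic antibiotic treatment of infection will be prescribed according to local standards". Section 6.3.4 repeats both sentences and refers back to 3.3.4. Section 6.4, which lists the modalities not allowed, does not mention systemic antibiotics.

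Infected ulcers are enrolled by design. Section 3.3.4 says that "in this trial wound infections will not be excluded. However, any subject with wound infection must be under treatment at the time of randomization". Section 6.3.4 admits mild and moderate infections. Section 4.1 accepts "University of Texas Grade 1A, 1B, 1C, 1D, 2A, 2B, 2C, or 2D (Appendix I"), and the classification table in Appendix I defines stage B as infected and stage D as "Infected and ischemic".

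Under section 3.1, every subject receives a diary card, and a study ID card, with its example in Appendix I, alerts other providers that the holder is in a trial.

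**The concern.** The card and the protocol give opposite instructions on the same treatment. The people who see the card are the ones least likely to have the protocol: the subject, a caregiver, or a clinician outside the study.

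The treatment matters because the protocol closes the other antimicrobial routes. Section 3.3.4 excludes antimicrobial dressings and local antimicrobials, and section 6.3.3 excludes antiseptic products at dressing changes. Local antiseptics appear only as wound preparation for the optional biopsies (section 8.2.5), which is not treatment of infection. Systemic antibiotics are therefore the only antimicrobial drugs available for an infected diabetic foot ulcer in this trial, and section 3.3.4 makes treatment of an existing infection a condition of randomization. Section 8.2.1 has the cards handed out at screening, before that point, and the schedule in 8.1.1 shows no visit between screening and baseline two weeks later.

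At stake is a delayed or withheld antibiotic when someone relies on the card between visits. This is a matter of subject safety and trial conduct, with no bearing on the statistical design.

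**Working it through.** No plan figure needs reproducing, and no formula applies. The check compares the texts item by item.

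**Step 1. The card's list against section 3.3.4.**

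| Group | Items on the card | Prohibited in 3.3.4? |
|---|---|---|
| Active dressings | antimicrobial dressings; enzyme dressings; growth factors (3) | yes, all 3, same order |
| Adjunctive treatments | hyperbaric oxygen; vacuum-assisted closure; heat; laser; mechanical constant tension; larval; artificial skin; electrical stimulation (8) | yes, all 8, same order |
| Last item | systemic antibiotic (1) | no; to be prescribed for infection |

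The card has 3 + 8 + 1 = 12 items. Matched to a prohibition: 3 + 8 = 11. Unmatched: 12 − 11 = 1. The count reads the card's *Heel* therapy as heat therapy and its *LS1R* as ESTR, since both look like damaged characters.

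**Step 2. Where the odd item sits.** The list in 3.3.4 closes with "Artificial Skin and Electrical stimulation for Tissue Repair (ESTR) are not allowed in this study". The card closes the matching run with the same two treatments in the same order. Section 6.4 names them in the reverse order, so 3.3.4 is the likelier source. The next thing 3.3.4 does is bar local antimicrobials and provide for systemic antibiotics. At that point the card has no general local-antimicrobial item and instead lists the permitted treatment as one to avoid. A slip in condensing those two sentences would produce this result. That explanation is inference; the mismatch does not depend on it.

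**Step 3. Section 6.4.** It lists 8 modalities: hyperbaric oxygen, vacuum-assisted closure, heat, laser, mechanical constant tension, larval therapy, electrical stimulation and artificial skin. None is a systemic antibiotic, so the card's item has no source there either.

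**Step 4. Does the item touch eligible subjects?** Grades 1A to 1D and 2A to 2D give 8 eligible grades. The infected ones are 1B, 1D, 2B and 2D, which is 4 of 8. This counts grades and does not estimate the share of subjects with infection, for which the documents give no figure.

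**Step 5. Is there any reconciling text?** None was found. No section limits systemic antibiotics in a way that would explain the card, and the card has no exception for infection.

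**The case against.** The strongest objection is that all the evidence comes from one example card whose available text is visibly damaged. Besides the odd spellings, the study name on the card differs from the title in the synopsis by a changed word and a missing one. A qualifier next to the antibiotic item could have been lost in the same way. This cannot be excluded, and it is why the original image has to be looked at first. However, the item is two intact words closed by a full stop, and nothing in the line points to missing text.

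Second, the card is labelled an example, says the treatments should be avoided rather than that they are not allowed, and leaves the operative rule in 3.3.4 and 6.3.4 clear for investigators. All true. But it is the only card wording in the protocol, and section 3.1 points to it. A patient or outside clinician who reads the item beside hyperbaric oxygen and vacuum therapy, with no exception, would take it as an instruction.

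Third, section 3.1 describes a diary card and an ID card separately, while the example is headed only as a diary card. The example seems to serve both purposes: its front has the participation notice, the list and the doctor to call, and its back has the diary. Reach to both subjects and providers is a reasonable reading, though it is not stated outright.

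Fourth, the route to harm is narrow. Infection is assessed at screening, at baseline and weekly through week 12, and the card names a doctor to call. These safeguards stand. They reduce the risk and leave the instruction wrong.

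**Conclusion.** The contradiction is real on the text as it stands. The example card tells its reader to avoid a treatment that two protocol sections say will be prescribed, in a trial that enrols infected ulcers and requires their infection to be under treatment at randomization. Its extent is one item of 12. The resulting risk cannot be put into numbers, and it is confined to subjects or outside providers who act on the card between visits.

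The conclusion assumes that the available text of the card is faithful on this item. Any practical consequence further assumes that the issued card carried the same words. Confidence is medium for those reasons. The point should be fixed because it is a safety-relevant instruction to subjects and is trivial to correct. It has no effect on sample size, the primary test or the data.

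**What to change.** 1. Check the wording on the original card image and on the card actually issued.
2. If the words are there, delete *systemic antibiotic* from the list. Alternatively, replace it with local (topical) antimicrobials and add that systemic antibiotics for infection are permitted. Either version agrees with 3.3.4 and 6.3.4; the second also supplies the general local-antimicrobial item that the card lacks.
3. If the issued card carries the words, reissue it and notify the ethics committees.

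The cost is two words on one card and, if it was issued in this form, one reprint with a notification. Sections 3.3.4, 6.3.4 and 6.4 need no change, and there is no design or analysis cost.

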4. EQ-5D

Under each heading, please tick the ONE box that best describes your health TODAY

MOBILITY

I have no problems in walking about
I have slight problems in walking about
I have moderate problems in walking about
I have severe problems in walking about
I am unable to walk about

SELF-CARE

I have no problems washing or dressing myself
I have slight problems washing or dressing myself
I have moderate problems washing or dressing myself
I have severe problems washing or dressing myself
I am unable to wash or dress myself

USUAL ACTIVITIES (e.g. work, study, housework, family or leisure activities)

I have no problems doing my usual activities
I have slight problems doing my usual activities
I have moderate problems doing my usual activities
I have severe problems doing my usual activities
I am unable to do my usual activities

PAIN / DISCOMFORT

I have no pain or discomfort
I have slight pain or discomfort
I have moderate pain or discomfort
I have severe pain or discomfort
I have extreme pain or discomfort

ANXIETY / DEPRESSION

[figure not shown]
I am not anxious or depressed
I am slightly anxious or depressed
I am moderately anxious or depressed
I am severely anxious or depressed
I am extremely anxious or depressed

UK (English) v.2 © 2009 EuroQol Group. EQ-5D™ is a trade mark of the EuroQol Group ²

- We would like to know how good or bad your health is TODAY.
- This scale is numbered from 0 to 100.
- 100 means the best health you can imagine.
0 means the worst health you can imagine.
- Mark an X on the scale to indicate how your health is TODAY.
- Now, please write the number you marked on the scale in the box below.

YOUR HEALTH TODAY =

The best health
you can imagine

The worst health
you can imagine

3
UK (English) v.2 © 2009 EuroQol Group. EQ-5D™ is a trade mark of the EuroQol Group

